### **Stage 3: Check**

The effectiveness of PDCA implementation was assessed through both process monitoring and outcome evaluation. Data collected from the intervention group were compared to baseline data from the control group.

Definitions:

Successful intubation: Independent completion of tracheal intubation by the resident following standard operating procedures.

Failed intubation: Three or more unsuccessful attempts to pass the endotracheal tube to appropriate depth.

Airway trauma: Presence of fresh blood in the airway post-intubation, excluding bleeding from preexisting pathology (e.g., subglottic mass, pulmonary hemorrhage).

Extubation failure due to airway injury: Need for reintubation within 72 hours despite meeting extubation criteria, confirmed by laryngoscopic evidence of edema, vocal cord paralysis, granulation, or subglottic stenosis.

Resident satisfaction: Evaluated via anonymous questionnaire covering

subjective learning experience and perceived value of training during their ED rotation.

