#### **六. Observation items and detection time points**

##### **1. First-Attempt Success Rate of Tracheal Intubation**

Observation item: Whether residents complete intubation successfully on the first attempt.

Detection time point: Immediately during the procedure, confirmed by chest

rise, end-tidal CO2, auscultation, or chest X-ray.

2. Intubation Completion Time

Observation item: Time required for residents to complete intubation.

Detection time point: Measured in seconds from insertion of the laryngoscope to confirmation of successful tube placement.

3. Incidence of Local Airway Trauma

Observation item: Presence of visible bleeding or mucosal injury during suctioning after intubation.

Detection time point: Within 24 hours post-intubation.

4. Extubation Failure Due to Airway Injury

Observation item: Need for reintubation caused by airway injury (edema, vocal cord paralysis, granulation, or subglottic stenosis).

Detection time point: Within 72 hours post-extubation.

5. Resident Satisfaction With Training

Observation item: Residents' subjective evaluation of the PDCA training program.

Detection time point: At the end of the emergency department rotation, via anonymous questionnaire.

七. standards for efficacy appraisal

1. Primary Efficacy Standard

First-attempt success rate of tracheal intubation is the primary indicator of efficacy.

An intervention is considered effective if the PDCA-trained group demonstrates a statistically significant improvement compared with the control group ( $P < 0.05$ ).

2. Secondary Efficacy Standards

Intubation completion time: A reduction in median time compared with controls indicates improved procedural efficiency.

Incidence of airway trauma and extubation failure: Lower rates suggest enhanced safety and procedural proficiency, even if not statistically significant.

Resident satisfaction score: Higher satisfaction rates reflect better training experience and improved confidence.

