### 3. Comprehensive Appraisal

The PDCA training program will be deemed efficacious if it results in significant improvement in the primary outcome and favorable trends across multiple secondary outcomes.

Statistical analyses will use chi-square tests for categorical variables and Mann-Whitney U test for continuous variables, with  $P < 0.05$  considered statistically significant.

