## 八. Observation of adverse events

### 1. Adverse Events of Interest

Local airway trauma: visible bleeding, mucosal laceration, or swelling during/after intubation.

Extubation failure due to airway injury: reintubation required within 72 hours caused by laryngeal edema, vocal cord paralysis, granulation tissue, or subglottic stenosis.

Procedure-related complications: hypoxemia ( $\text{SpO}_2 < 90\%$ ), aspiration, esophageal intubation, dental injury, or hemodynamic instability (e.g., hypotension, arrhythmia).

Resident-related adverse events: psychological distress, fatigue, or stress-related reactions during high-risk airway procedures.

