### 3. Recording and Reporting

All adverse events will be recorded in case report forms (CRFs), specifying type, severity, onset time, and outcome.

Serious adverse events (SAEs) will be reported to the institutional ethics committee within 24 hours.

Data will be analyzed to compare incidence rates between the control and PDCA groups.

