### 十. Statistical processing

All statistical analyses were performed using SPSS version 26.0 (IBM Corp., Armonk, NY, USA). Categorical variables, including intubation success rate,

incidence of local airway trauma, extubation failure due to airway injury, and resident satisfaction rate, were expressed as counts and percentages [n (%)], and were compared between groups using the chi-square test ( $\chi^2$  test) or Fisher's exact test, as appropriate. Continuous variables, such as intubation completion time, were tested for normality using the Shapiro–Wilk test. Variables not conforming to a normal distribution were expressed as median (interquartile range) and compared using the Mann–Whitney U test. A two-tailed P value  $< 0.05$  was considered statistically significant.

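### Protocol section 七.2 reads any numerically lower rate of airway trauma or extubation failure as a sign of better safety, waiving the test that section 十 sets for the same outcomes

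*Protocol*

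**What the plan says.** Section 七, item 2 (Secondary Efficacy Standards), fixes in advance how two harm outcomes are to be read: "Incidence of airway trauma and extubation failure: Lower rates suggest enhanced safety and procedural proficiency, even if not statistically significant".

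Section 十 (Statistical processing) lists the same outcomes among the categorical variables: "incidence of local airway trauma, extubation failure due to airway injury, and resident satisfaction rate, were expressed as counts and percentages". They are compared between groups by chi-square or Fisher's exact test, and the threshold is given as "A two-tailed P value" below 0.05.

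Section 七, item 3 (Comprehensive Appraisal), calls the programme efficacious if the primary outcome improves significantly and there are "favorable trends across multiple secondary outcomes".

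Other harms are handled in section 八. Item 1 lists hypoxaemia and also "aspiration, esophageal intubation, dental injury, or hemodynamic instability". Item 3 says: "Data will be analyzed to compare incidence rates between the control and PDCA groups".

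**The concern.** Two parts of the protocol give different standards for one comparison. Section 十 tests the two outcomes. Section 七.2 then says that the favourable reading stands whether or not the test is passed. The rule is also one-sided, since 七.2 gives no reading for a higher rate. For the primary outcome, section 七.1 does require significance, so the waiver applies to outcomes that measure harm.

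A report that follows 七.2 could say that PDCA training points to better safety when the data on these outcomes fit equally well with no difference or with an increase in injury. The same falls could then be counted among the trends that 七.3 asks for.

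**Working it through.** The protocol gives no event rate, effect size or power for these outcomes, so there is no stated figure to reproduce. The check asks how often the 七.2 condition, a lower rate in the PDCA group, is met when there is no benefit.

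**Inputs**
- From the protocol: 100 cases (Abstract); two-sided 0.05 level and chi-square or Fisher's exact test (section 十); a lower rate is sufficient (section 七.2).
- Assumed: 50 per group; independent binomial counts; airway trauma rate 10% to 30%; extubation failure rate 2% to 10%.

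**Step 1. Chance of a lower rate.** With X_C ~ Bin(50, p_C) and X_T ~ Bin(50, p_T), P(lower) = Σ over t < c of P(X_C = c) × P(X_T = t).

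*No true difference (p_T = p_C):*

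| True rate | P(PDCA lower) |
|---|---|
| 2% | 0.345 |
| 6% | 0.415 |
| 10% | 0.433 |
| 20% | 0.450 |
| 30% | 0.457 |

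The remainder is ties plus the mirror image. At 2%, for example, 0.345 + 0.309 (tie) + 0.345 ≈ 1.

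*PDCA truly worse:*

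| Control → PDCA | P(PDCA lower) |
|---|---|
| Trauma 10% → 15% | 0.180 |
| Trauma 20% → 25% | 0.235 |
| Trauma 30% → 35% | 0.260 |
| Extubation failure 2% → 4% | 0.179 |
| Extubation failure 6% → 8% | 0.276 |
| Extubation failure 10% → 12% | 0.315 |

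**Step 2. Sensitivity to the assumed size.** With no true difference, splits from 30/70 to 70/30, or 100 per group, give 0.396 to 0.517. If only 30 per group reach extubation, extubation failure at 2%, 6% and 10% gives 0.290, 0.388 and 0.413.

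**Step 3. What such a result looks like.** Newcombe 95% interval for d = p_T − p_C, with Wilson limits (l, u) for each group: lower = d − √[(p_T − l_T)² + (u_C − p_C)²]; upper = d + √[(u_T − p_T)² + (p_C − l_C)²].
- Trauma 8/50 against 10/50: d = 0.16 − 0.20 = −0.04. The Wilson limits are 0.083 to 0.285 and 0.112 to 0.330. Lower = −0.04 − √(0.077² + 0.130²) = −0.191; upper = −0.04 + √(0.125² + 0.088²) = +0.113. Fisher P = 0.80.
- Extubation failure 1/50 against 2/50: d = −2.0 points, interval −11.6 to +7.0, Fisher P = 1.00.

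Both results meet the 七.2 condition, although an increase of 11 points in the first and 7 points in the second is not excluded.

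**Step 4. The same question under the section 十 test.** I summed the Step 1 products over tables where PDCA is lower and P < 0.05, using chi-square, or Fisher's exact test where an expected count is below 5. With no true difference the chance is 0.0002, 0.007, 0.020, 0.026 and 0.025 at 2%, 6%, 10%, 20% and 30%. Under a true reduction it is 0.30 for trauma 20% → 10% and 0.03 for extubation failure 6% → 2%.

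**The case against.** The sentence is hedged: it speaks of suggestion, admits that the result may not be significant, and concerns secondary outcomes. Section 十 still has counts, percentages and a test reported, so a reader would see the P value. All of this stands and limits the consequence. It does not remove the fault, because a direction that arises about a third to nearly half of the time by chance is weak ground even for a hedged statement agreed in advance.

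Three stronger readings are tempting, and the documents do not support them.
- *The study could be declared positive on trends alone.* Section 七.3 also requires a significant primary outcome. The 0.35 to 0.46 is the chance of a lower rate on one outcome, not the study's false-positive rate.
- *Safety is to be judged on local airway injury only.* Both outcomes are indeed local; trauma, for instance, is defined as "Airway trauma: Presence of fresh blood in the airway post-intubation, excluding bleeding from preexisting pathology". But 七.2 names its outcomes openly and nowhere says that safety rests on them alone. Section 八 records the wider harms and compares them between groups, and nothing tells the reader to ignore that comparison. A cross-reference is worth adding, but this is not a separate fault.
- *The probabilities are properties of the protocol.* They rest on an assumed split and assumed rates, and the protocol does not say whether a case is a resident or an intubation.

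It can also be said that the 七.2 lines on completion time and satisfaction set no significance requirement either. That is true, but only the trauma and extubation line expressly waives it.

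**Conclusion.** The point holds as a fault of interpretation. Section 七.2 pre-sets a favourable reading of two harm outcomes and waives the two-tailed test that section 十 assigns to them. With 50 per group and the event rates above, all assumed, the condition is met with probability about 0.35 to 0.46 under no true difference and 0.18 to 0.31 under modest true harm. Under the planned test, the null chance of claiming a reduction falls to at most about 0.026 per outcome. Other splits and sizes move the first range only to about 0.29 to 0.52, so the conclusion does not depend on the exact assumptions.

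A non-significant fall is inconclusive: it shows neither better safety nor less local injury. What is at stake is one unsupported statement in the report, and its use as a trend in 七.3. The efficacy conclusion itself is not at stake. A wording correction is warranted.

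**What to change.** In section 七.2, delete the clause that waives significance and replace the sentence with:

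> Airway trauma and extubation failure will each be reported as a between-group difference with 95% CI and the section 十 test. A reduction in local airway injury will be claimed only if that test is significant (two-tailed P < 0.05); otherwise the result will be described as inconclusive, with its interval. Any wider safety statement will also refer to the adverse-event comparison in section 八.3.

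In section 七.3, add that a non-significant fall in these two outcomes does not count as a favourable trend that shows safety.

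The claim should hang on the section 十 test and not on whether the interval excludes zero, because the two can disagree when events are few. With 0/50 against 5/50 the Newcombe upper limit is about −0.9 points, while Fisher's exact test gives P = 0.056.

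The change costs a few sentences and needs no new data or endpoint. The downside is that most real reductions will be reported as inconclusive with about 100 cases: by Step 4, even a true halving of trauma from 20% to 10% would be claimed only about 30% of the time. By the usual two-proportion formula, that halving would need 199 per group for 80% power.

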statistical method	All statistical analyses were performed using SPSS version 26.0 (IBM Corp., Armonk, NY, USA). Categorical variables, including intubation success rate, incidence of local airway trauma, extubation failure due to airway injury, and resident satisfaction rate, were expressed as counts and percentages [n (%)], and were compared between groups using the chi-square test ( $\chi^2$ test) or Fisher's exact test, as appropriate. Continuous variables, such as intubation completion time, were tested for normality using the Shapiro–Wilk test. Variables not conforming to a normal distribution were expressed as median (interquartile range) and compared using the Mann–Whitney U test. A two-tailed P value $< 0.05$ was considered statistically significant.

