## 二、 research objective

This study aims to evaluate the impact of a PDCA cycle-based tracheal intubation training model for EM residents. We hypothesize that such structured, iterative, and feedback-driven training can significantly enhance intubation success, procedural efficiency, safety, and trainee confidence in high-stakes emergency environments.

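### A non-significant lower rate of airway trauma or extubation failure is read in advance as a safety gain, setting aside the protocol's own two-tailed test

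*Protocol*

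**What the plan says.** **The planned test.** The abstract's statistical method names "incidence of local airway trauma, extubation failure due to airway injury, and resident satisfaction rate" among the categorical variables. Section 十 (Statistical processing) repeats the list and says these variables "were compared between groups using the chi-square test" or Fisher's exact test, with two-tailed P<0.05 as the criterion. Section 七, item 3 (Comprehensive Appraisal) says it again: "Statistical analyses will use chi-square tests for categorical variables".

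**The reading rule.** Section 七, item 2 (Secondary Efficacy Standards) says of airway trauma and extubation failure: "Lower rates suggest enhanced safety and procedural proficiency, even if not statistically significant".

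**Higher rates.** Section 七 is silent. Section 八, item 3 says only: "Data will be analyzed to compare incidence rates between the control and PDCA groups".

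**The hypothesis.** Section 二 expects that the training "can significantly enhance intubation success, procedural efficiency, safety, and trainee confidence".

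**The verdict.** Section 七, item 1 says: "An intervention is considered effective if the PDCA-trained group demonstrates a statistically significant improvement compared with the control group". Item 3 asks for "significant improvement in the primary outcome and favorable trends across multiple secondary outcomes".

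**The concern.** A test is planned for two safety outcomes, and a null result from it is set aside in advance if the difference lies in the hoped-for direction. No section limits this reading to description, asks for an interval, or sets a smallest difference that would count.

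The hypothesis includes a significant gain in safety. Followed as written, the report could give a favourable safety reading from a chance difference, although the data do not rule out a material increase in airway injury.

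There is also a lesser point of clarity. Item 1 of section 七 judges effectiveness on the primary outcome alone, while item 3 adds favourable trends on several secondary outcomes. They can be read together as a primary standard plus an overall appraisal. However, the text does not say which governs the study's conclusion, what counts as a trend, or how many outcomes are needed. The main point does not depend on this.

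**Working it through.** The protocol gives no event rate, effect size or power for these outcomes, so there is no figure of its own to reproduce. The check is how often the clause would come into play.

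**Inputs**

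- Total of 100 cases (abstract). The unit (residents or intubations) and the split between groups are not stated. *Assumed:* 50 independent intubations per group, then splits from 30:70 to 70:30.
- Two-tailed 0.05 by chi-square or Fisher (abstract and section 十).
- *Assumed* control event rates: 1%, 2%, 5%, 10% and 20%.

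**Formula.** Let X be the events among n_C control cases and Y the events among n_P PDCA cases, as independent binomials. The clause applies when Y/n_P < X/n_C and P ≥ 0.05. Its probability is the sum, over all such pairs (x, y), of Bin(x; n_C, p_C) × Bin(y; n_P, p_P).

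**Results, 50 per group**

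| Control rate | No difference: PDCA lower, any P | No difference: lower and P≥0.05, Fisher | Same, uncorrected chi-square | 1.5-fold increase under PDCA: lower and P≥0.05, Fisher | Same, uncorrected chi-square |
|---|---|---|---|---|---|
| 1% | 0.267 | 0.267 | 0.266 | 0.219 | 0.219 |
| 2% | 0.345 | 0.345 | 0.339 | 0.250 | 0.246 |
| 5% | 0.406 | 0.403 | 0.385 | 0.231 | 0.225 |
| 10% | 0.433 | 0.424 | 0.408 | 0.179 | 0.176 |
| 20% | 0.450 | 0.436 | 0.424 | 0.100 | 0.099 |

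Comparing the second and third columns, nearly every lower result under no difference is a non-significant one, so the clause covers almost all of them.

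**Other splits (30:70, 40:60, 60:40, 70:30, with 50:50), both tests**

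- No difference: 0.234 (70 PDCA, 30 control, 1%, chi-square) to 0.514 (30 PDCA, 70 control, 5%, Fisher).
- 1.5-fold increase: 0.099 (50:50, 20%, chi-square) to 0.367 (30 PDCA, 70 control, 2%).

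**Worked example: 4/50 PDCA against 5/50 control**

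- Difference: 0.08 − 0.10 = −0.02.
- Chi-square: pooled rate 9/100 = 0.09; z = 0.02 / √(0.09 × 0.91 × 2/50) = 0.35; P = 0.73. Fisher P = 1.00.
- Wilson limits: PDCA 0.032 to 0.188; control 0.043 to 0.214.
- Newcombe lower limit: −0.02 − √[(0.08 − 0.032)² + (0.214 − 0.10)²] = −0.144.
- Newcombe upper limit: −0.02 + √[(0.188 − 0.08)² + (0.10 − 0.043)²] = +0.102.

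The data are compatible with anything from 14 points fewer to 10 points more airway injury, yet section 七 would read them as pointing to better safety.

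**The case against.** The strongest reply is that nothing is contradicted. The statistical section defines significance and does not forbid describing a non-significant difference. The clause uses a soft verb and says openly that significance may be lacking, and the P value would still be reported beside it. The primary test is untouched. All of this is true. But the sentence stands among the standards for appraising efficacy, and its last clause serves only to allow a favourable reading without statistical support.

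Second, an adverse direction is not ignored. Section 八 lists both outcomes as adverse events of interest and requires recording and serious-event reporting. Section 九 requires cumulative review of adverse events. A higher rate would also not be a favourable trend under item 3 of section 七. These are monitoring and overall-appraisal provisions; none tells the report how to interpret an uncertain difference.

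Third, the neighbouring standards on completion time and satisfaction also rest on direction alone, so deleting one clause would not cure the list. This stands. It means the interval rule does most of the work in the fix.

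Fourth, with no true difference any direction-only statement comes out favourable somewhat under half the time once ties are removed, so 27% to 44% is close to a truism. The inputs are assumed, and at a 1% control rate the 1.5-fold case is 0.5 against 0.75 expected events per 50. This is fair: the figures show how little direction says at this size. They are not an error rate for a formal claim.

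Finally, interval reporting may be left to an analysis plan not shown here. The objection, however, is to a rule that the protocol states, not to a missing detail.

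**Conclusion.** The concern holds. The protocol fixes in advance a favourable safety reading that its own planned test may fail to support, and nothing in the document confines that reading to description.

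With 50 independent cases per group, the clause would apply to each outcome in 27% to 44% of studies with no true difference (Fisher; 27% to 42% by chi-square). It would still apply in about 10% to 25% if PDCA raised the rate 1.5-fold. Across the splits examined, the ranges widen to 23% to 51% and 10% to 37%.

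The event rates, the split, the unit behind the 100 cases and independence are all assumptions. Repeated intubations by one resident would change the figures but would not turn an uncertain difference into evidence of safety. The damage is limited to the safety and proficiency statements; the overall verdict is not inflated. The change should be made, but it does not threaten the primary analysis.

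**What to change.** In section 七, item 2:

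- Delete the clause that waives statistical significance.
- State that airway trauma and extubation failure will be reported as risk differences with 95% confidence intervals, whichever direction they take.
- State that improved safety will be claimed only if the interval excludes no difference, and that the result will otherwise be called inconclusive.

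The completion-time and satisfaction lines could be brought under the same reporting principle, each with a suitable effect measure.

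As a clarification, say which of items 1 and 3 of section 七 governs the study's conclusion. If the trend condition stays, define which outcomes count, how many are needed, and what makes a trend favourable.

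The cost is wording only, with no new data. The safety statement will be less favourable when events are few.

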### 3. Comprehensive Appraisal

The PDCA training program will be deemed efficacious if it results in significant improvement in the primary outcome and favorable trends across multiple secondary outcomes.

Statistical analyses will use chi-square tests for categorical variables and Mann-Whitney U test for continuous variables, with  $P < 0.05$  considered statistically significant.

## 八. Observation of adverse events

### 1. Adverse Events of Interest

Local airway trauma: visible bleeding, mucosal laceration, or swelling during/after intubation.

Extubation failure due to airway injury: reintubation required within 72 hours caused by laryngeal edema, vocal cord paralysis, granulation tissue, or subglottic stenosis.

Procedure-related complications: hypoxemia ( $\text{SpO}_2 < 90\%$ ), aspiration, esophageal intubation, dental injury, or hemodynamic instability (e.g., hypotension, arrhythmia).

Resident-related adverse events: psychological distress, fatigue, or stress-related reactions during high-risk airway procedures.

